3.3 Removal of Subjects from Study

Subjects may be withdrawn from the study for the following reasons:

- At their own request or at the request of their legally acceptable representative
- If, in the investigator's opinion, continuation in the study would be detrimental to the subject's well-being
- At the specific request of the sponsor

Also, subjects must be withdrawn for the following reasons:

- A significant violation of the protocol, as determined by the sponsor or the investigator
- Highly significant abnormalities in the laboratory results (Highly significant abnormalities generally follow lab related exclusion criteria, but a PI can determine the high significance on any abnormalities for the safety of subject)
- Use of any other investigational drugs
- Subjects enrolled in the current trial but taking any prohibited medication/therapy stated in the inclusion/exclusion criteria
- Subject enrolled in the current trial but having a baby

If a subject prematurely withdraws from the study, the subject must return to the clinical site for the early termination visit. In all cases, the reason for withdrawal must be recorded in the electronic Case Report Form (eCRF) and in the subject's medical records.

Contact will be maintained with subjects who are removed due to an adverse event (AE) until it has been resolved or stabilized, and the information will be documented in the eCRF and in the subject's medical records.

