3.5.6 Randomization and Blinding

As this is a double-blinded study, blinding of the drug contents from the subjects, investigators, and other study personnel at each clinical site is necessary. Because two syringes of AstroStem and control are different, one physician must be only assigned to the role of syringe injection in order to maintain the double-blinding against other site physicians and staffs.

After the eligibility is confirmed, a subject will be assigned with one randomization code using the electronic data capture (EDC) system on Visit 2 (Week -4). A randomization code is assigned into one of two groups.

A code-break envelope for each subject including the randomization code information will be retained by each site and can be opened, revealing the randomization information, for emergency purposes only. Investigator should note that the occurrence of a SAE should not routinely precipitate immediate unblinding. An attempt to contact the sponsor must be made prior to unblinding. If unblinding occurs, the subject must be early terminated; a written explanation must be prepared immediately.

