SAP Version 1 was created and approved prior to first patient visit and any unblinding of the study team.

2. Study Objectives

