4.6. Treatment Group Comparability

4.6.1. *Patient Disposition*

Subject disposition information will be summarized for all subjects. Summaries will include: the number of subjects in each analysis population, the number of subjects completed the study, and the number of subjects discontinued study and its reason. All subjects randomized in the study will be included in the summary table. Patient allocation by investigator or site will be summarized. Patient allocation by investigator or site will also be listed as well.

4.6.2. *Protocol Deviations*

Listings of subjects with significant protocol deviations or violations will be provided. The following list of significant protocol violations will be determined from the clinical database and from the study clinical/medical group:

- Lack of informed consent or late informed consent
- Violations of inclusion/exclusion criteria
- Significant violations of prohibited concomitant medication usage as determined by the clinical/medical group
- Other significant protocol violations as determined by the clinical/medical group

4.6.3. *Patient Characteristics*

The following patient characteristics at baseline will be summarized by treatment group for all ITT patients:

- Demographic (age, gender, ethnic origin, height, weight, BMI)
- Medical history and Pre-existing condition

Medical history and pre-existing conditions will be summarized by preferred term (PT) within system organ class (SOC). Medical history is defined as illness(es) that ended prior to the signing of informed consent. Pre-existing conditions and AEs at baseline are those AEs occurring during the baseline/screening visits that is Visit 1, 2 and 3.

4.6.4. *Prior and Concomitant Therapy*

Verbatim terms on eCRFs will be mapped to Anatomical Therapeutic Chemical (ATC) class and Generic Drug Names using the World Health Organization (WHO) Drug Dictionary Enhanced (WHODDE) B2 format, March 1, 2015 release.

Prior medications are defined as medications started to take prior to the first injection. Concomitant medications are defined as medications started on or after the day of first injection of the study drug during the study.

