Prior and concomitant medications will be tabulated for the ITT population by WHODDE ATC level 2 classifications, preferred term, and treatment. If a subject reports the same preferred term multiple times, then the frequency of that preferred term will only be incremented by one. As with the preferred term, if a subject reports multiple medications within the same ATC level 2 classification, then the frequency of that ATC level 2 classification will only be incremented by one. Percentages will be calculated using the total number of subjects in the safety population. Each summary will be ordered by descending order of incidence of preferred term within each ATC class. Prior and concomitant medications will be included in a data listing.

4.6.5. *Treatment Compliance*

Not applicable.

4.7. *Efficacy Analyses*

The primary efficacy hypothesis test will be performed using a 5% significance level. For the secondary efficacy endpoints, hypothesis tests will be performed individually at the 5% significance level. All hypothesis tests will be performed with two-sided alternative hypotheses. No adjustments on the significance level for multiple comparisons are planned, as this is a phase 1/2 study. All efficacy analyses will be based on the ITT population.

4.7.1. *Primary Efficacy Analysis*

The primary objective of this study is to test the hypothesis that AstroStem is superior to placebo in the improvement on neurological/neurocognitive assessment from baseline to week 30 in patients with Alzheimer's Disease.

The primary analysis will evaluate the efficacy of AstroStem compared with placebo on the overall mean change from baseline to week 30 in ADAS-Cog score. The primary efficacy variable will be summarized with means, standard deviations, medians and ranges, overall and by group. The change from Baseline ADAS-Cog score will be analyzed with Student's t-test or Kruskal-Wallis test depending on the violation of normality assumption.

4.7.2. *Secondary Efficacy Analyses*

The secondary efficacy analyses will be summarized with means, standard deviations, medians and ranges for continuous variables including the changes from baseline at Week 30 in MMSE, CDR-SOB, NPI, GDS and ADCS-ADL.

These changes score from baseline at week 30 will be analyzed with Student's t-test or Kruskal-Wallis test depending on the violation of normality assumption. .

4.7.3. *Exploratory Efficacy Analyses*

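### Subjects removed as significant protocol violators before Week 30 are missing from the primary ITT comparison, because Section 3.3 takes them out of the study and not only off treatment

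*Protocol*

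**What the plan says.** Protocol 3.3 has two lists. The permissive one includes removal "At the specific request of the sponsor", with no criterion. The mandatory one opens "Also, subjects must be withdrawn for the following reasons" and includes "A significant violation of the protocol, as determined by the sponsor or the investigator". Section 3.3 does not define significant. After premature withdrawal "the subject must return to the clinical site for the early termination visit". Continued contact is promised only to subjects removed for an adverse event.

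SAP 4.7 states: "All efficacy analyses will be based on the ITT population". ITT (Protocol 6.1.1.1, SAP 4.3.1) requires at least one injection and post-injection efficacy data, and it does not exclude violators. SAP Table 5 gives Visit 3 as baseline and Visit 13 as the postbaseline observation for the primary analysis. Nothing is imputed (Protocol 6.1.8; SAP 4.5 and 4.10). The per-protocol set is the ITT subjects who complete Visit 13, and criteria may be added before unblinding (Protocol 6.1.1.2, SAP 4.3.2).

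On blinding, Protocol 3.5.6 says "blinding of the drug contents from the subjects, investigators, and other study personnel at each clinical site is necessary". The sponsor is not named.

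SAP 4.6.2 provides for listings of subjects with significant violations, including "Violations of inclusion/exclusion criteria".

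**The concern.** An ITT comparison is meant to keep subjects in the arm to which they were randomised, whatever happens afterwards. Here a rule of conduct works against that. Someone judges a violation significant, the subject leaves the study, the Week 30 ADAS-Cog is not collected, and the primary test has no value for that subject. The exclusion depends on judgment, comes after randomisation, and may be made by the sponsor. With 11 subjects per arm, each one lost is about 9% of an arm (1/11).

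Two things are at stake. One is precision, which is lost however the removal comes about. The other is bias, which arises if removal is related to both arm and prognosis. That does not require anyone to know the allocation: a violation may itself be more likely in one arm, for example if it depends on how the subject is faring.

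**Working it through.** **What happens to a removed subject**

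1. A significant violation is judged before Visit 13, and withdrawal from the study is mandatory (Protocol 3.3).
2. The subject attends an early termination visit (Protocol 3.3 and 4.4). ADAS-Cog is taken there, but no Week 30 assessment is provided for.
3. The primary analysis reads Visit 13 only (SAP Table 5). The SAP uses Early Termination scores only in the exploratory analyses (SAP 4.7.3).
4. Nothing is imputed, so the subject has no value in the primary test.
5. The subjects left in the ITT test at Week 30 are those with a Visit 13 score. The per-protocol set is the ITT subjects who completed Visit 13. Unless per-protocol criteria are added, the two are nearly the same people.

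**Where this stops.** A violation judged between Weeks 30 and 52, or at database review, comes after the score exists, and no text deletes it. A violation not judged significant triggers nothing.

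**Size.** The only planned figure is the sample size, 11 + 11 = 22, which agrees (Protocol 6.2). No SD, effect size or dropout rate is given, so results are in SD units and the number removed is an assumption.

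*Removal unrelated to arm and outcome.* The 95% half-width of the arm difference is t(0.975, n1 + n2 − 2) × √(1/n1 + 1/n2):

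| Subjects with a Week 30 score | t | √(1/n1 + 1/n2) | Half-width (SD) |
|---|---|---|---|
| 11 v 11 | 2.086 | 0.4264 | 0.889 |
| 10 v 11 | 2.093 | 0.4369 | 0.915 |
| 10 v 10 | 2.101 | 0.4472 | 0.940 |

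The interval is wider by 0.915/0.889 = 1.03 or 0.940/0.889 = 1.06, that is 3% to 6%. In 400,000 simulated trials with no true effect, random removal of one to three subjects from one arm left the mean difference at 0.001 SD and two-sided rejection at 5.0% to 5.1%.

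*Removal related to arm and prognosis.* In the same simulation (normal data, 11 per arm, no true effect), removing the AstroStem subject with the poorest Week 30 change shifted the difference by 0.158 SD in favour of AstroStem. This is an upper bound for one subject, because it selects on the Week 30 change itself, which does not exist when a removal before Visit 13 is decided. If selection is on an earlier measure, the expected shift is multiplied by that measure's correlation with the Week 30 change. At an assumed correlation of 0.5 it is 0.158 × 0.5 = 0.079, about 0.08 SD. At zero it vanishes.

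**The case against.** Several stronger readings are tempting, and the case against them is good.

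- **The ITT comparison holds only non-violators.** A reader might infer this, but the ITT definition excludes no violator, late or minor violations leave the score in place, and SAP 4.6.2 expects significant violators in the database and only lists them. The loss comes through missing Week 30 data.
- **Every item in SAP 4.6.2 forces removal.** That list is for reporting and rests with the clinical/medical group. The trigger in 3.3 is a judgment by the sponsor or investigator. The two share a term, but no text joins them.
- **The sponsor is unblinded.** The documents are silent. The study is called double-blind, code-break envelopes are kept at the sites for emergencies, the unblinded interim safety look goes to an independent monitor, and SAP section 1 says the plan was approved "prior to first patient visit and any unblinding of the study team", which implies a blinded study team. The laboratory that supplies cells or saline must be able to tell the arms apart, but 3.3 gives it no part in withdrawals. What stands is that no clause binds the sponsor staff who may decide them.
- **The false-positive rate rises sharply.** Dropping the poorest AstroStem scorer moves simulated rejection in AstroStem's favour from 2.5% to 6.1%, but only by choosing on a score not yet observed. It is not a prediction.
- **No analysis could recover the loss.** ADAS-Cog is taken at Visits 6, 9 and 12 and at early termination, and a longitudinal model could use those scores. The plan has none, and even such a model would rest on assumptions about the unobserved Week 30 value.

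It is also fair to say that any dropout before Visit 13 is lost in the same way. This case is distinct because the plan orders the loss, on a judgment, for subjects who might have been willing to return.

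**Conclusion.** The point holds in this limited form. Section 3.3 turns a judged significant violation, or an unexplained sponsor request, into removal from the study. When that happens before Visit 13, the subject is omitted from the primary Week 30 comparison even though the analysis is called ITT.

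The certain cost is modest: a 3% to 6% wider interval for one subject lost from one arm or from each. The possible cost is a bias of at most about 0.16 SD for one removal, and about 0.08 SD at an assumed correlation of 0.5. These figures assume normal data with equal SDs, no true effect, and one removal from AstroStem. The documents give no removal rate, so how often this would happen is unknown. Nothing in them shows that the sponsor would know the arm or use the power selectively; the weakness is that the plan does not rule it out. The phase 1/2 label does not settle the matter, because SAP 4.7.1 states a superiority hypothesis and SAP 4.7 tests it at 5%. The change is worth making because it is cheap and must be in place before the visits are missed.

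**What to change.** 1. In Protocol 3.3, with a matching sentence in 4.4, state that a subject who has given valid consent and is removed for a protocol violation, or at the sponsor's request for a non-safety reason, is still asked to attend the scheduled efficacy assessments at Visits 13 and 14.
2. In Protocol 6.1.1.1 and SAP 4.3.1, state that these subjects are analysed in their randomised arm for ITT. The present definition, at least one injection with later efficacy data, still applies.
3. Use significant violations only to define the per-protocol set, fixed before unblinding. Protocol 6.1.1.2 and SAP 4.3.2 already allow added criteria. One is needed here, because a violator who attends Visit 13 would otherwise count as per protocol.
4. Require a documented reason for each sponsor-requested removal, decided by staff without access to the randomisation codes, and extend the blinding requirement in 3.5.6 to those staff.

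Rules on stopping treatment and on safety withdrawal are left unchanged. The cost is wording, plus attendance by removed subjects at visits already in the schedule. The small downside is that ITT will include some deviating subjects; the per-protocol set then shows the result without them.

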3.4 Premature Termination of Study / Closure of Center

The sponsor has the right to terminate this study, and the investigator/sponsor has the right to close a clinical site, at any time, although this should occur only after consultation between involved parties; the IRB must be informed in any case. Should the clinical site be closed prematurely, all study materials (equipment, study medication, etc.) must be returned to the sponsor.

This study will discontinue due to medical or administrative reasons such as:

- Serious adverse events probably related to study drug administration so that the use of study drug may no longer be justifiable
- 2 or more deaths are observed during any point in the trial
- Significant change of benefit-risk ratio for the subjects
- Sponsor discontinues the investigation of AstroStem for the treatment of Alzheimer's Disease or determines that the doses being studied are no longer justifiable

Possible reasons for closing of a clinical site include the following:

- The investigator feels that the number or severity of adverse events is excessive
- A change of technical, administrative, or personal circumstances occurs and the conduct of the study no longer meets ICH-GCP guidelines
- In case of evident, significant non-compliance to protocol or poor data quality

3.5 Treatment

3.5.1 Treatment to be Administered

At Visit 2 (Week -4), a subject, who is qualified for this study, will be randomized to one of two study groups and the adipose tissue will be harvested via liposuction. At Visits 3 through 12, the randomized subject will receive a single intravenous injection per visit.

3.5.2 Identity of Investigational Product

AstroStem is in a 20 ml syringe including AdMSCs as 1×10^8 cells/10mL of saline with 30% auto-serum and is stable at refrigerated condition (+2 to +8 °C) up to 1 week. A negative control syringe including saline with 30% auto-serum will be packed by the aluminum foil pack to be matched with AstroStem syringe in appearance to be indistinguishable.

3.5.3 End of Study

The efficacy results will be analyzed when the last subject completes Visit 13 (Week 30 follow-up) and this study is finished when the last subject completes Visit 14 (Week 52 follow-up).

3.5.4 Selection of Dose in Study

The dosage of AstroStem was chosen through pre-clinical study published in PLOS One [14].

3.5.5 Choice of Control/Comparator

This study uses saline with 30% auto-serum as a control.

3.5.6 Randomization and Blinding

As this is a double-blinded study, blinding of the drug contents from the subjects, investigators, and other study personnel at each clinical site is necessary. Because two syringes of AstroStem and control are different, one physician must be only assigned to the role of syringe injection in order to maintain the double-blinding against other site physicians and staffs.

After the eligibility is confirmed, a subject will be assigned with one randomization code using the electronic data capture (EDC) system on Visit 2 (Week -4). A randomization code is assigned into one of two groups.

A code-break envelope for each subject including the randomization code information will be retained by each site and can be opened, revealing the randomization information, for emergency purposes only. Investigator should note that the occurrence of a SAE should not routinely precipitate immediate unblinding. An attempt to contact the sponsor must be made prior to unblinding. If unblinding occurs, the subject must be early terminated; a written explanation must be prepared immediately.

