3.5.7 Prior and Concomitant Treatments

If the use of any concomitant treatment(s) becomes necessary, the treatment(s) must be recorded in the eCRF, including the name of the drug or treatment, dose, route of administration, date and time of the treatment, and indication. In the event that concomitant medication is administered, the principal investigator or qualified sub-investigator must assess the subject's eligibility of continuing the participation in the study.

The following medications/therapies are not allowed to be taken/used by subjects enrolled in this study during the trial (up to Week 52, a final follow-up visit):

- Any investigational drug
- Any therapy that may affect Alzheimer's disease, in the judgment of the investigator
- Immunosuppressant
- Cytotoxic drug
- Corticosteroids or similar steroid anti-inflammatory medication (e.g., Prednisone) on a regular basis (exceptions allowed include; regular use of steroid nasal sprays, topical steroids, and estrogen-replacement therapy)

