4.4 Early Termination Visit

If a subject will drop-out the study before Visit 14 (Week 52), the clinical site will try to schedule an early termination visit. During this visit, the following assessments and procedures should be performed:

- The following questionnaires will be completed: ADAS-Cog (see Appendix 2), MMSE (see Appendix 3), CDR-SOB (see Appendix 4). NPI (see Appendix 5), GDS (see Appendix 6), ADCS-ADL (see Appendix 7) and C-SSRS (see Appendix 8).
- Measure vital signs (sitting blood pressure, pulse, breathing, and temperature) and weight.
- Perform a complete physical examination.
- Measure 12-lead ECG.
- Record any changes in concomitant medications.
- Record any adverse events, if applicable.
- Collect blood and urine samples for hematology, serum chemistry, pregnancy test (only for women of childbearing potential), biomarker analysis and urinalysis.
- Perform MRI scan including FLAIR and T2- weighted gradient-echo sequences.

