7.2.2 Adverse Event Severity

The severity of adverse events should be graded as follows:

- Mild – Usually transient in nature and generally not interfering with normal activities
- Moderate – Sufficiently discomforting to interfere with normal activities
- Severe – Prevents normal activities

Medically significant adverse events considered related to the study drug by the investigator or Sponsor will be followed until resolved or considered stable.

It will be left to the investigator’s clinical judgment to determine whether an adverse event is related and of sufficient severity to require the subject’s removal from treatment or from the study. A subject may also voluntarily withdraw from treatment due to what he or she perceives as an intolerable adverse event. If either of these situations arises, the subject should be strongly encouraged to undergo an end-of-study assessment and be under medical supervision until symptoms cease or the condition becomes stable.

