7.4 Procedures for Managing Microhemorrhages and Cerebral Vasogenic Edema

MRI scan will be performed at screening, Visit 9 (Week 12), Visit 13 (Week 30), Visit 14 (Week 52), and/or Early Termination Visit. The protocols for MRI scans should include fluid-attenuation inversion recovery (FLAIR) and T2-weighted gradient-recalled-echo (GRE) sequences. Standards for the detection of cerebral microhemorrhage or superficial siderosis will include: 2D T2 GRE; field strength of 1.5 Tesla or greater; slice thickness of 5mm or less; Echo Time (TE) of 20 ms or greater. Standard FLAIR sequences are generally appropriate for the detection of cerebral vasogenic edema.

Subjects who are found to have new clinically asymptomatic microhemorrhages will be followed up closely, and a follow-up MRI will be done to evaluate the stability of those lesions.

All Principal Investigators will be notified of the possible occurrence of cerebral vasogenic edema, its imaging manifestations, and the clinical signs and symptoms that may accompany this phenomenon. They will also be told of the measures to be taken if cerebral vasogenic edema occurs. Those measures will include more frequent serial MRI scans until the imaging abnormalities resolve, and consideration of treatment with high-dose dexamethasone if symptoms are severe.

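### Unblinding, marked laboratory abnormality and prohibited medication end study participation, so the Week 30 and 52 assessments are dropped for subjects picked out by safety-related triggers

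*Protocol*

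**What the plan says.** Three rules remove a subject from the study.

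- **Unblinding** (Protocol 3.5.6): "If unblinding occurs, the subject must be early terminated; a written explanation must be prepared immediately".
- **Laboratory findings** (Protocol 3.3, under the reasons for which withdrawal is mandatory): "Highly significant abnormalities in the laboratory results". The investigator has some discretion over what qualifies.
- **Prohibited medication** (same list): "Subjects enrolled in the current trial but taking any prohibited medication/therapy stated in the inclusion/exclusion criteria". Section 3.5.7 has its own list of disallowed treatments, which applies "during the trial (up to Week 52, a final follow-up visit".

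What follows removal is described in two ways. Section 3.3: "If a subject prematurely withdraws from the study, the subject must return to the clinical site for the early termination visit". Section 4.4: "If a subject will drop-out the study before Visit 14 (Week 52), the clinical site will try to schedule an early termination visit".

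Protocol 7.2.2 recognises removal from treatment as distinct from removal from the study, but for both it says that "the subject should be strongly encouraged to undergo an end-of-study assessment". Section 3.5.8 has all subjects returning at Weeks 30 and 52.

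For cerebral vasogenic edema, Protocol 7.4 lists "more frequent serial MRI scans until the imaging abnormalities resolve, and consideration of treatment with high-dose dexamethasone if symptoms are severe".

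SAP 4.4 (Table 5) takes Visit 13 as the only postbaseline observation for the primary efficacy analysis. Protocol 6.1.8 and SAP 4.5 and 4.10 plan no imputation.

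**The concern.** Stopping infusions and leaving the study are separate decisions. The first protects the subject; the second also ends scheduled observation. Sections 3.3 and 3.5.6 make the second follow automatically from the trigger. The subjects concerned have needed an emergency code break, have a marked laboratory change, or have started a prohibited treatment, so they are not a random subset. Safety is a primary endpoint (Protocol 3.6.1), and late safety information would be thinnest in subjects for whom it may matter most. The same rules remove the primary efficacy value of anyone taken out before Week 30, for reasons that may be related to outcome.

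**Working it through.** **1. What each rule acts on**

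| Trigger | Where | Mandatory? | Ends study participation? | Visits 13 and 14 kept? |
|---|---|---|---|---|
| Code broken | 3.5.6 | Yes | Yes | Not stated |
| Highly significant laboratory abnormality | 3.3 | Yes, once so judged | Yes | Not stated |
| Medication prohibited by the eligibility criteria | 3.3 | Yes | Yes | Not stated |
| Adverse event, investigator's judgment | 7.2.2 | No | Treatment or study | Not stated |
| Reaction to the previous infusion | 4.2.2 to 4.2.6 | Governs the repeat injection | Not stated | Not stated |

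The first three rows are the point. The last two show that the protocol contemplates a subject who is off infusions, but no section gives that subject a visit path. Section 3.5.8 does not supply one: read literally, it conflicts with the removal rules and does not qualify them.

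**2. What remains after removal**

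- One early termination visit with questionnaires (including ADAS-Cog and C-SSRS), vital signs, physical examination, ECG, laboratory tests, biomarkers, MRI and adverse events (4.4). It is compulsory in 3.3 and best effort in 4.4.
- Contact until resolution or stabilization, for subjects removed because of an adverse event (3.3). Removal for unblinding or medication alone is not clearly covered.
- SAE follow-up to resolution or stabilization, and reporting without time limit of events judged related or of unknown relationship (7.3). The general window is 30 days after the last dose, 30/7 = 4.3 weeks. Section 7.3 also mentions the follow-up period, so capture of later unrelated SAEs after removal is unclear.

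The scheduled Week 30 and 52 MRI, laboratory tests, ECG, C-SSRS and ADAS-Cog are not among these.

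**3. Primary efficacy value**

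A subject removed before Week 30 has no Visit 13 score. An early termination ADAS-Cog may exist, but SAP 4.7.3 places it in the exploratory analyses. With no imputation, the subject drops out of the primary comparison. Removal after Week 30 does not affect it.

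**4. Size**

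The plan has no figure to reproduce here. Protocol 6.2 gives 11 per arm without a formal calculation.

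- One removal: 1/11 = 9.1% of an arm. Two (an assumption): 2/11 = 18.2%.
- Time with no infusion left to stop: 52 − 18 = 34 weeks, or 34/52 = 65% of the period from baseline.
- Illustration: a subject unblinded at Week 4 leaves 52 − 4 = 48 weeks of the planned schedule.

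**5. Effect on late safety information (assumed losses and rates)**

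With n subjects followed and no late event seen, the one-sided 95% upper bound is 1 − 0.05^(1/n). The chance of seeing at least one late event at true rate p is 1 − (1 − p)^n.

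| Still followed in an arm | Upper bound, zero events | p = 5% | p = 10% | p = 20% | p = 30% |
|---|---|---|---|---|---|
| 11 | 23.8% | 43% | 69% | 91% | 98% |
| 9 | 28.3% | 37% | 61% | 87% | 96% |
| 7 | 34.8% | 30% | 52% | 79% | 92% |

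These figures treat removals as random. If removed subjects are more prone to late findings, the true loss is larger.

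**6. Section 7.4 against exclusion 17, 3.5.7 and 3.3**

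Exclusion 17 and 3.5.7 bar corticosteroids when used regularly, a term left undefined. Section 3.3 withdraws users of medication barred by the criteria. Section 7.4 contemplates dexamethasone and serial MRI without saying whether the subject stays in the study. Two sites could class the same course differently and reach opposite conclusions about continued participation.

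**The case against.** The case against is substantial and limits the point in four places where a reader might infer more.

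- *Every safety event removes the subject.* The documents do not say so. Section 7.2.2 allows removal from treatment alone, and the check before each repeat injection states no study withdrawal.
- *Safety follow-up is lost altogether.* It is not. The early termination visit is a full assessment, and 3.3 and 7.3 keep specific follow-up open. What is lost is the scheduled later assessments.
- *Decline leading to new Alzheimer's therapy forces withdrawal.* Such therapy is disallowed in 3.5.7 but is not among the criteria that 3.3 cites. Withdrawal would depend on the sponsor or investigator judging it a significant protocol violation.
- *Sections 3.3 and 7.4 flatly contradict each other.* They conflict only if a course given under 7.4 counts as regular use. Otherwise both can be followed, and serial MRI until resolution is not expressly limited to subjects still in the study.

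It is also fair that no removal rate is given, that 3.5.6 discourages routine unblinding after an SAE, and that the laboratory rule is reserved for highly significant findings. Removals may therefore be few.

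The unblinding and laboratory rules still stand: once triggered they are mandatory, they end participation, and neither stops applying after the last infusion. Few removals are also enough to matter with 11 per arm.

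**Conclusion.** The concern holds for the three mandatory removal rules. As written, they end scheduled observation at an early termination visit for subjects selected by safety-related triggers. Removal before Week 30 also costs the primary value. Each case is 9% of an arm. After Week 18, removal ends the remaining scheduled data collection once the early termination visit is done, without stopping any infusion. How many subjects this would affect cannot be derived from the documents; the bounds and detection chances above rest on assumed losses and event rates. For subjects off infusions by other routes, the defect is an unstated visit path. For section 7.4, it is an undefined term with consequences for study status.

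**What to change.** In Protocol 3.3, 3.5.6, 4.4 and 7.2.2, leave the sponsor's triggers for stopping infusions unchanged, and state that stopping infusions or being unblinded does not by itself end data collection. Such subjects have the early termination assessments at that point and are still asked to attend Visits 13 and 14 unless they withdraw consent. Record the event and its date as an intercurrent event. Align 3.3 with 4.4 on whether the early termination visit is required or attempted, and make 3.5.8 consistent with both.

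Separately, reconcile 7.4 with exclusion 17, 3.5.7 and 3.3: define what counts as regular corticosteroid use, and state whether a subject treated under 7.4 remains in the study. Which answer is right is a clinical matter for the sponsor; none is proposed here.

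The cost is amendment wording and, for a few subjects, two visits that are already planned. The downside is that some Week 30 and 52 values will come from subjects who are off infusions or unblinded. These must be flagged, and the SAP should say how they are handled in the primary comparison.
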